2. STUDY SCHEME

[figure not shown]

Figure 1: CLINICAL STUDY SCHEME

3. SCIENTIFIC BACKGROUND

3.1 OVERVIEW

OpRegen consists of retinal pigment epithelium (RPE) cells that were produced by directed differentiation of a human embryonic stem cell (hESC) line and are suspended in injection solution to be implanted subretinally.

The Sponsor intends to carry out a Phase I/IIa study of OpRegen in subjects with GA, the advanced form of dry-AMD, to address the safety of this therapeutic cell formulation product and to obtain initial indications of any potentially clinically significant efficacy.

This clinical trial will be conducted in accordance with the standards of Good Clinical Practice (GCP) and International Conference on Harmonization guidelines, applicable government regulations and the institutional research policies and procedures. This protocol along with the Investigators' Brochure, Informed Consent and other supporting documentation will be submitted to the Institutional Review Board (IRB) and regulatory authorities, for review and formal approval prior to subject enrollment.

4. BACKGROUND

4.1 PROPOSED INDICATION

AMD is a progressive chronic disease of the central retina and a leading cause of vision loss worldwide. Most visual loss occurs in the late stages of the disease due to one of two processes: neovascular ("wet") AMD and geographic atrophy (GA, "dry"). In GA, progressive atrophy of the retinal pigment epithelium, choriocapillaris, and photoreceptors occurs (Lim, et al. 2012). The dry form of AMD is more common (85-90% of all cases), but may progress to the "wet" form, which, if left untreated, leads to rapid and severe vision loss (Nowak 2006).

The pathogenesis of the disease involves abnormalities in four functionally interrelated tissues, RPE, Bruch's membrane, choriocapillaris and photoreceptors. However, impairment of RPE cell function is an early and crucial event in the molecular pathways leading to clinically relevant AMD changes (Nowak 2006). Refer to the Investigator's Brochure, Section 1.1.1 for more information.

4.2 THE RETINAL PIGMENT EPITHELIUM AND ITS CHARACTERISTICS

Description and characteristics of RPE cells are presented in the Investigator's Brochure in Section 1.1.2.

4.3 TREATMENT APPROACHES

There is currently no effective or approved treatment for dry-AMD. Prophylactic measures include vitamin/mineral supplements. These reduce the risk of developing wet AMD but do not affect the development or progression of GA.

There are currently no FDA approved treatments for GA secondary to AMD. GA is a chronic, progressive condition that leads to central blind spots and often, permanent loss of vision.

The development of several investigational agents has been halted because of disappointing results, however intensive AMD research continues, raising hopes for improved treatments. Though multifactorial, the underlying mechanism of non-neovascular AMD (dry-AMD) is the death of RPE cells. The RPE comprise a single layer of cells, which perform many functions necessary for healthy photo transduction (Strauss O 2005) and any dysfunction in these activities may lead to vision loss. Cell transplantation of healthy RPE to replace dystrophic or lost RPE has been considered a potential therapy to preserve or even restore vision loss.

The Sponsor uses a GMP-compliant hESC line, ethically approved for inclusion in the NIH Human Embryonic Stem Cell Registry, for derivation of the RPE cells, using the directed differentiation approach, described in the subsequent section.

4.3.1 Background on hESC Derived RPE Cells

Two general approaches have been used to obtain RPE cells from hESCs, spontaneous differentiation and directed differentiation. More information regarding hESC derived RPE cells can be found in section 1.1.3 of the Investigator's Brochure.

4.3.2 Derivation of OpRegen

As described in the IB (Section 1.1.3), the transplantation of RPE cells has long been considered as a possible therapy for attenuating disease progression and improving vision in AMD (Binder S, Stanzel BV, et al. 2007, da Cruz L, et al. 2007, Lund RD, et al. 2006). hESCs can serve as a potential unlimited source of RPE cells that may overcome the restrictions of limited supply. An overview of the Sponsor's directed differentiation protocol can be found in Section 2.4 of the IB.

[REDACTED]

The rationale for key study design components is provided in the following sections.

6.1 STUDY POPULATION

The rationale for the study population is based on the Sponsor's goal of testing of the safety and exploration of the efficacy of OpRegen in subjects with dry-AMD. For the sake of safety and for ethical reasons, the first three cohorts include legally blind subjects with BCVA of 20/200 or less. The fourth study cohort includes subjects with BCVA between 20/64 and 20/250, where measures of GA progression and changes in visual acuity and other functional outcomes may be more efficiently applied and interpreted.

6.2 COHORT SIZE

The proposed cohort size is comparable with the expected amount of risk and should be sufficient to demonstrate safety and tolerability of OpRegen in the chosen population. Exploration of the efficacy measures will be performed in the fourth cohort of approximately 12 subjects (12 eyes) and may be used in designing the future clinical studies of OpRegen.

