8.1.1 Number of Subjects

Approximately 24 subjects will be enrolled in four cohorts, with three subjects enrolled in each of the first two cohorts, up to 6 subjects in the third cohort, and approximately 12 subjects enrolled in the fourth cohort.

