22. STATISTICAL METHODOLOGY

22.1 STUDY DESIGN AND SAMPLE SIZE

As this is an open-label, phase I/IIa dose escalation, safety, tolerability and preliminary efficacy study, neither power assessment, nor formal hypotheses testing are currently planned for study outcome measures.

Detailed methodology for data summary and analyses will be documented in a Statistical Analysis Plan (SAP). This document may modify the plans outlined in the protocol; however, any major modification of the outcome measures and/or its analysis will also be reflected in a protocol amendment. Additional statistical analyses other than those described in this section may be performed if deemed appropriate and included in the SAP.

The planned sample size of approximately 24 eyes for 4 study cohorts to be treated with targeted OpRegen® doses of 50×10^3 and up to 200×10^3 cells, is considered clinically appropriate for further characterization of the safety, tolerability and preliminary efficacy of OpRegen® in the treatment of subjects with subjects with advanced dry-form AMD with GA.

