22.2 ANALYSIS SETS

22.2.1 Modified Intent-to-Treat (mITT) Analysis Set

The Modified Intent-to-Treat (mITT) analysis set will consist of all subjects who have been enrolled to the trial and received the OpRegen® implantation. This analysis set, which will include all data captured in database for these subjects, will serve as the primary Analysis Set for inference.

22.2.2 **Per Protocol (PP) Analysis Set**

The Per Protocol (PP) analysis set is a subset of the mITT Analysis Set and will consist of all subjects who have been enrolled into the trial, received the OpRegen® implantation and violated none of the major protocol guidelines.

22.3 **SIGNIFICANCE LEVEL**

No formal hypothesis testing is planned for this study. However, a significance level of 0.05 using two-tailed tests will be utilized in the case that exploratory significance testing will be performed.

22.4 **INTERIM REPORTS**

Comprehensive interim reports of accumulated safety, tolerability and preliminary available efficacy data will be presented to the independent Data Safety Monitoring Board (DSMB).

Depending on the safety data available, there will be a DSMB recommendation to pursue one of the following alternatives: proceed to the next higher dose; stop dose escalation; investigate a lower dose; or repeat a dose level.

22.5 **DESCRIPTIVE STATISTICS**

All measured variables and derived parameters will be listed individually and if appropriate, presented in summary tables by dose regimen group and overall, providing sample size, absolute and relative frequency for categorical variables, or sample size, arithmetic mean, standard deviation, median, minimum and maximum for continuous variables. Confidence intervals will be presented for the efficacy endpoints for exploratory purposes only.

22.6 **MISSING DATA**

Every effort will be made to complete follow-up for all subjects and avoid missing data, in particular regarding essential items. For other cases of missing data, the “last observed value” (LOV) approach will be used when appropriate.

22.7 **SUBJECT DISPOSITION**

Data from subjects who are screened but not treated, subjects in the mITT and PP Analysis Sets, as well as trial withdrawals from study follow-up will be summarized using descriptive statistics.

22.8 **DEMOGRAPHIC AND BASELINE CHARACTERISTICS**

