22.13 HYPOTHESIS

The primary hypothesis is that there will be no dose-limiting toxicity (DLT) and that implantation of OpRegen[®] to subjects with progressive dry-form AMD with GA will be safe and well-tolerated.

For the purpose of this study DLT is defined as an SAE determined to be product-related.

A secondary null hypothesis is that there will be no difference in disease progression, as measured by retinal function and structure, between the treated and untreated regions in the treated eye and between treated and untreated eye of a subject.

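### Protocol 6.2 says the cohort size should be enough to demonstrate safety; zero events in 3, 6, 12 or 24 eyes leaves two-sided 95% upper limits of 71%, 46%, 26% or 14%, and no safety interval is planned to show this

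*Protocol*

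**What the plan says.** Protocol 6.2, the section that gives the rationale for cohort size, says the size "should be sufficient to demonstrate safety and tolerability of OpRegen in the chosen population". It gives no event rate, precision or probability of detection.

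Protocol 8.1.1 sets the numbers: "Approximately 24 subjects will be enrolled in four cohorts". The split is 3, 3, at most 6 and about 12. SAP 4.0 reports 3, 3, 6 and 12 subjects, all treated.

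Protocol 22.1 says that "neither power assessment, nor formal hypotheses testing are currently planned for study outcome measures". Like SAP 6.0, it describes the size as clinically appropriate for characterizing safety further. Protocol 22.13 and SAP 3.3 nevertheless state a primary hypothesis: that no dose-limiting toxicity (DLT) will occur and that implantation will be safe and well tolerated.

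On intervals, Protocol 22.5 says: "Confidence intervals will be presented for the efficacy endpoints for exploratory purposes only". SAP 6.0 and 6.4 repeat this. SAP 8.0 adds that safety variables get no inferential statistics unless specified otherwise. Under SAP 10.0, categorical summaries show only categories in which someone had a response, and a computed 0% is left blank.

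**The concern.** Safety is the primary objective, and the primary hypothesis is one that a table with no events would appear to confirm. Read beside 6.2, such a table invites the conclusion that safety has been shown. With 3 to 12 eyes per cohort, a zero count is compatible with true rates that few readers would call safe.

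Protocol 22.14 and SAP 7.0 do warn that the numbers are too small for a definitive assessment, but only for the secondary hypothesis on retinal structure and function. The primary safety hypothesis carries no such warning, and the planned safety tables contain nothing that quantifies the limitation.

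**Working it through.** **The plan's own figure.** The cohort sizes add up: 3 + 3 + 6 + 12 = 24. No power, precision or detection calculation is given, so there is nothing further to reproduce.

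**Inputs.**
- n = 3, 6, 12 and 24, from Protocol 8.1.1 and SAP 4.0.
- Confidence level: neither document sets one for safety. I use two-sided 95%, in line with the two-tailed 0.05 level that Protocol 22.3 and SAP 6.2 give for exploratory testing, and show one-sided 95% beside it.

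**Upper limit when no event is seen.** The chance of no event in n subjects at true rate p is (1 − p)^n. The exact (Clopper-Pearson) upper limit is the p at which this chance equals 0.025 (two-sided) or 0.05 (one-sided):

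upper limit = 1 − 0.025^(1/n), or 1 − 0.05^(1/n)

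For n = 12, two-sided: 1 − 0.025^(1/12) = 1 − 0.7354 = 0.2646. For n = 24: 1 − 0.025^(1/24) = 0.14247.

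| Eyes, zero events | Two-sided 95% upper limit | One-sided 95% upper limit |
|---|---|---|
| 3 (Cohort 1 or 2) | 70.8% | 63.2% |
| 6 (Cohort 3) | 45.9% | 39.3% |
| 12 (Cohort 4) | 26.5% | 22.1% |
| 24 (all, pooled) | 14.2% | 11.7% |

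**Chance of missing an event type altogether.** The documents give no expected rate. The 5% and 10% below are assumptions for illustration. Chance of no event = (1 − p)^n:

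| Assumed true rate | 12 eyes | 24 eyes |
|---|---|---|
| 5% | 0.95^12 = 54% | 0.95^24 = 29% |
| 10% | 0.90^12 = 28% | 0.90^24 = 8% |

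**What the reader of the report would see.** Take an event type with no occurrence in Cohort 4. The column header carries N = 12. Under SAP 10.0 the row is either omitted or has a blank percentage. Under SAP 8.0 no interval accompanies it. The 26.5% limit appears nowhere.

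**The case against.** The strongest reply is that small unpowered cohorts are usual in phase I/IIa, that descriptive safety reporting was a deliberate choice (SAP 8.0), and that the governing statistical text in Protocol 22.1 and SAP 6.0 is already modest. On this view the fault is one verb, hedged by *should be*, in a rationale section. Escalation rests on DSMB review and event-count rules, not on interval estimates. Much of this stands: 22.1 needs no change to its wording on characterization, and the sample size is not in question.

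Four stronger readings are tempting, and the documents do not support them.

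- *The sample size is miscalculated.* No calculation is made, and no figure in the documents is wrong.
- *Protocol 22.5 expressly confines intervals to efficacy.* In that sentence *only* most naturally limits the purpose to exploration. That no safety interval is planned follows from the silence on safety there, together with SAP 8.0.
- *Nothing in the output would reveal a small denominator.* Column totals and individual listings are planned, and adverse events are tabulated by cohort. What is missing is the uncertainty around a zero, and SAP 10.0 may remove the zero itself.
- *A clinically unacceptable rate is left open.* The documents set no threshold. Protocol 6.2 refers to an expected amount of risk, but the risk summary is redacted, so its basis cannot be judged.

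It is also true that the SAP describes all 24 subjects as treated, so rewording 6.2 cannot affect enrolment. The reporting change can still matter: SAP 2.0 allows revision before database lock, and SAP 9.0 plans a final analysis at Year 5.

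**Conclusion.** The point holds as an overstated claim together with a reporting gap. Protocol 6.2 attributes to the cohort size a capacity that it does not have and that 22.1 does not claim. With zero events, the two-sided exact 95% limits run from 70.8% for a three-eye cohort to 14.2% for all 24 eyes. Using one-sided limits (63% to 12%) does not change the conclusion.

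Three conditions apply. The limits hold only if no event is seen; any event raises them. The confidence level is my choice. The 14.2% figure treats one rate as common to doses, two formulations, two delivery devices and two vision strata. A reader might take it as a bound for each dose or device, which it is not; it is the most favourable case.

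Nothing here suggests that the product is unsafe or that the trial should have been larger.

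**What to change.** 1. **Protocol 6.2.** Replace *demonstrate* with *provide an initial characterization of*, and state the zero-event upper limits for 3, 6, 12 and 24 eyes with their confidence level. Leave the characterization wording in 22.1 as it is.
2. **Protocol 22.5 and SAP 6.4.** Add descriptive exact (Clopper-Pearson) 95% intervals for the proportion of subjects with DLT, with a treatment-emergent SAE and, where applicable, with a device AESI, by cohort and overall. Label the overall interval as pooled across doses, formulations, devices and vision strata.
3. **SAP 8.0 and 10.0.** Add matching exceptions to the rule on inferential statistics for safety variables and to the blank-zero and empty-category rules, so that 0/n and its upper limit are printed for these events.

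The table list in SAP 11 has a serious-event table, but no title there names DLT or device AESI, so a short added table or a few rows would be needed. Otherwise the cost is wording and a less favourable stated claim. No more patients and no new data are required.

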6.3 STUDY ENDPOINTS

The measures chosen to evaluate the safety and tolerability of OpRegen and the surgical procedure during and after implantation take into account the cellular characteristics of OpRegen and the implantation procedure. Clinical endpoints include rate of GA progression, retinal sensitivity to light and changes in visual acuity. These measures are acceptable in the ophthalmology field for assessment of retinal and macular function in dry-AMD with GA ([O'hEineachain R](#)).

6.4 DOSAGE

The clinical targeted dosages of up to 200×10^3 are considered feasible based on the results of the pre-clinical studies.

[REDACTED]

[REDACTED]

6.5 STAGGERED ENROLLMENT

The targeted doses of 50×10^3 and up to 200×10^3 cells will be implanted sequentially, with staggered intervals as follows:

- In the first cohort there will be a staggered interval of six weeks between the first and second subjects, and four weeks between the second and third subjects.

[REDACTED]

[REDACTED]

After the meeting, the DSMB will provide their recommendation for cohorts 1-3 to pursue one of the following alternatives: proceed to the next higher dose; stop dose escalation; investigate a lower dose; or repeat a dose level.

Based on the previous pre-clinical experience and common clinical practice with dry-AMD subjects and cell-therapy treatments, proposed staggered intervals should allow monitoring and investigation of adverse events, prior to exposure of additional subjects to the product. The staggered interval between cohorts and subjects allows sufficient safety assessment prior to exposing subjects to the next higher dose of OpRegen and before initiation of treating subjects with better visual function.

6.6 SUBRETINAL ROUTES OF ADMINISTRATION

6.6.1 Vitrectomy and Retinotomy

The subretinal implantation of cells is customarily accomplished with a conventional partial vitrectomy followed by retinotomy. Pars plana vitrectomy (PPV) has become an important tool in vitreoretinal surgery and in the treatment of retinal disease. The traditional 3-port procedure is well-known to retina specialists and is performed with microsurgical equipment resulting in incisions that are usually self-sealing. The vitreous is gently removed with a vitreous cutter and the cell suspension of OpRegen is implanted subretinally through a small retinotomy. The wound is self-healing. The procedure can be visualized through the dilated pupil with a special wide-field lens. Although vitrectomy is useful to diagnose and treat many retinal diseases, it is not without challenge, most notably clouding of the lens as a result of perturbations to the vitreous and potential egress of implanted cells through the retinotomy site until healed.

[REDACTED]

7. STUDY OBJECTIVES, HYPOTHESIS AND STUDY ENDPOINTS

7.1 HYPOTHESIS

Implantation of OpRegen to subjects with advanced dry-form AMD with GA is safe, well-tolerated and provides preliminary efficacy evidence.

7.2 STUDY OBJECTIVES

7.2.1 Primary Objectives

To evaluate the safety and tolerability of human embryonic stem cell-derived retinal pigment epithelium cells (OpRegen), transplanted subretinally to subjects with advanced dry age-related macular degeneration (AMD) with geographic atrophy (GA).

7.2.2 Secondary Objectives

To evaluate the preliminary efficacy of OpRegen treatment by assessing the changes in ophthalmological parameters as measured by various methods of primary clinical relevance.

7.3 STUDY ENDPOINTS

7.3.1 Safety and Tolerability Endpoints

Safety and tolerability of OpRegen treatment will be assessed by:

- Incidence and frequency of treatment emergent AEs
- Treatment emergent changes in the following variables:
 - Vital signs
 - Hematology/ Blood Chemistry/Urinalysis
 - Physical examination

- Ophthalmological evaluations including:
 - ✓ BCVA
 - ✓ Dilated Fundus Exam
 - ✓ IOP
 - ✓ SLE
 - ✓ SD-OCT
 - ✓ FA
 - ✓ Microperimetry
 - ✓ FAF
 - ✓ CFP

[REDACTED]

[REDACTED]

[REDACTED]

[REDACTED]

[REDACTED]

- [REDACTED]
- [REDACTED]
- [REDACTED]

[REDACTED]

- [REDACTED]

7.3.4 Efficacy Endpoints of Clinical Relevance

Preliminary efficacy assessments will utilize the below listed parameters:

- Directional change in the GA lesion area over time
- Overall change in the GA lesion area of the study eye over time using SD-OCT and FAF
- Change from baseline over time in BCVA as measured by ETDRS chart
- Change from initial assessment over time in retinal sensitivity (as assessed by microperimetry)
- Change from baseline over time in Reading Speed Test
- Change from baseline over time in Low Luminance BCVA

- Correlation assessment between quantitative metrics derived from FAF, SD-OCT and CFP images
- Correlation assessment between functional and structural changes
- Change over time in NEI VFQ-25 Quality of Life score
- Change over time in Functional Reading Independence (FRI) Index score

8. STUDY POPULATION

8.1 SUBJECTS CHARACTERISTICS

The subjects who will be enrolled for this clinical trial are males and females, 50 years of age and older, who were diagnosed with dry (non-neovascular) AMD in both eyes. The subjects will be enrolled in four cohorts. The first three cohorts will include subjects with visual acuity equal or less than 20/200 in the study eye. A fourth cohort will include subjects with visual acuity between 20/64 and 20/250 in the study eye.

8.1.1 Number of Subjects

Approximately 24 subjects will be enrolled in four cohorts, with three subjects enrolled in each of the first two cohorts, up to 6 subjects in the third cohort, and approximately 12 subjects enrolled in the fourth cohort.

8.1.2 Special Populations

There is no specific goal for gender inclusion/exclusion in this clinical trial, therefore no individual will be excluded from participation based on gender. In case women of childbearing age are participating in this study, they must have two negative pregnancy tests within one month prior to study agent implantation and must agree to use effective contraception for one year following implantation of OpRegen.

No clinically significant sex/gender differences in the intervention effect are expected. There is no intent to exclude from participation based on race and/or ethnicity.

8.2 ELIGIBILITY CRITERIA FOR COHORTS 1-3

8.2.1 Inclusion Criteria

1. Age 50 and older.
2. Diagnosis of dry (non-neovascular) age related macular degeneration in both eyes.
3. Funduscopy findings of dry AMD with progressive geographic atrophy in the macula,
[REDACTED]
4. Best corrected central visual acuity equal or less than 20/200 in the study eye by ETDRS vision testing.
5. Vision in the non-operated eye must be better than or equal to that in the operated eye.

6. Subjects with sufficiently good health to allow participation in all study-related procedures and complete the study follow-up period (based on medical records).
7. Ability to undergo a vitreoretinal surgical procedure under monitored anesthesia care.
8. Blood counts, blood chemistry, coagulation and urinalysis without abnormal significance.
9. Negative for HIV, HBC, and HCV. Negative for CMV IgM and EBV IgM.
10. Willing to defer donation of blood and tissues.
11. Able to understand study procedures and willing to sign informed consent

